
 Proportion of subjects with a HAQ-DI decrease of at least 0.35 at Weeks 16, 24 and 52 compared to baseline in subjects with HAQ-DI >0.35 at baseline Change in physical function as assessed by HAQ-DI change from baseline to Weeks 16, 24 and 52 Proportion of subjects achieving MDA at Weeks 16, 24 and 52 Change in DAPSA and cDAPSA at Weeks 16, 24 and 52 as compared to baseline Proportion of subjects achieving VLDA at Weeks 16, 24 and 52 Change in quality of life as assessed by SF-36 total score, physical component summary (PCS), and mental component summary (MCS) change from baseline to Weeks 16, 24 and 52 	
 HAQ-DI response at Weeks 16, 24 and 52 HAQ-DI change from baseline to Week 16, 24 and 52 MDA at Weeks 16, 24 and 52 DAPSA/cDAPSA change from baseline to Week 16, 24 and 52 VLDA at Weeks 16, 24 and 52 Change in SF-36 total score, PCS, and MCS at Weeks 16, 24 and 52

To investigate the durability of response after Weeks 16 in subjects on izokibep 160mg QW and Q2W who achieved the primary and secondary endpoints at W16
	
ACR50, PASI 90, LEI, MDA, ACR20, and PsAID responses at Weeks 24 and 52

To investigate the incremental response after Week 16 in subjects in all treatment groups (izokibep 160mg QW, izokibep Q2W and placebo/izokibep cross-over) who did not achieve the primary and secondary endpoints at Week 16
	
ACR50, PASI 90, LEI, MDA, ACR20, and PsAID responses at Weeks 24 and 52

To investigate the relationship between ACR50 response and other factors
 
 Association of baseline WPI positive WPI ≥ 7 with ACR50 response 	
 Baseline positive WPI ≥ 7 and ACR50 response

Objectives	Endpoints

To investigate that the 80 mg Q4W regimen is efficacious compared to placebo, as measured by the same primary, secondary and exploratory endpoints
 
To compare the three regimens of izokibep for assessment of dose-response relationships, as measured by the primary and secondary endpoints
	

To evaluate the pharmacokinetics of izokibep in subjects with psoriatic arthritis
 
To evaluate the immunogenicity of izokibep in subjects with PsA
	
 • Trough plasma concentrations of izokibep at collected timepoints • Presence of anti-drug antibodies (positive or negative)

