
To investigate whether 1 or both regimens of izokibep (160 mg QW and 160 mg Q2W) are efficacious compared to placebo up to Week 16 and to estimate the efficacy of each regimen after week 16 in the subpopulation with enthesitis as baseline, as measured by:
 
 • Proportion of subjects achieving an improvement in PsAID of at least 3 units at Weeks 16, 24 and 52 compared to baseline in subjects with PsAID ≥ 3 at baseline • Change from baseline in PsAID at Weeks 16, 24 and 52 • Proportion of subjects with a HAQ-DI decrease of at least 0.35 at Weeks 16, 24 and 52 compared to baseline in subjects with HAQ-DI >0.35 at baseline • Change in physical function as assessed by HAQ-DI change from baseline to Weeks 16, 24 and 52 • Proportion of subjects achieving MDA at Weeks 16, 24 and 52 • Change in DAPSA and cDAPSA at Weeks 16, 24 and 52 as compared to baseline • Proportion of subjects achieving VLDA at Weeks 16, 24 and 52 • Change in quality of life as assessed by SF-36 total score, physical component summary (PCS), and mental component summary (MCS) change from baseline to Weeks 16, 24 and 52 • To investigate the durability of response after Weeks 16 in subjects on izokibep 160mg QW and Q2W who achieved the primary and secondary endpoints at W16 	
 • PsAID response at Weeks 16, 24 and 52 • PsAID change from baseline to Week 16, 24 and 52 • HAQ-DI response at Weeks 16, 24 and 52 • HAQ-DI change from baseline to Week 16, 24 and 52 • MDA at Weeks 16, 24 and 52 • DAPSA/cDAPSA change from baseline to Week 16, 24 and 52 • VLDA at Weeks 16, 24 and 52 • Change in SF-36 total score, PCS, and MCS at Weeks 16, 24 and 52 
ACR50, PASI 90, LEI, MDA, ACR20, and PsAID responses at Weeks 24 and 52
 
ACR50, PASI 90, LEI, MDA, ACR20, and PsAID responses at Weeks 24 and 52

Objectives	Endpoints

To investigate the incremental response after Week 16 in subjects in all treatment groups (izokibep 160mg QW, izokibep Q2W and placebo/izokibep cross-over) who did not achieve the primary and secondary endpoints at Week 16
	
 Baseline positive WPI ≥ 7 and ACR50 response

To investigate the relationship between ACR50 response and other factors
 
 Association of baseline WPI positive WPI ≥ 7 with ACR50 response 	

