- Mean (median) Area under the curve (AUC) for ACR-N through week 16
- Change from baseline in LEI at Weeks 16, 24 and 52
- Time to first achievement of ACR50

- Time to first achievement of PASI90 among subjects with at least 3% BSA at baseline
- Time to first achievement of MDA
- Time to first achievement of ACR20
- Time to first achievement of PsAID improvement of at least 3 among subjects with PsAID at least 3 at baseline
- Time to first achievement of PASI100 among subjects with at least 3% BSA at baseline
- To investigate whether 1 or both regimens of izokibep (160 mg QW and 160 mg Q2W) are efficacious compared to placebo, in the subpopulation with enthesitis as baseline, as measured by:
  - Proportion of subjects achieving an improvement in PsAID of at least 3 units at Week 16 compared to baseline in subjects with PsAID  $\geq 3$  at baseline
  - Change from baseline in PsAID at Week 16
  - Proportion of subjects with a HAQ-DI decrease of at least 0.35 at Week 16 compared to baseline in subjects with HAQ-DI  $>0.35$  at baseline (Response to HAQ-DI at Week 16)
  - Change in physical function as assessed by HAQ-DI change from baseline to Week 16
  - Proportion of subjects achieving MDA at Week 16
  - Change in DAPSA and cDAPSA at Week 16 as compared to baseline
  - Proportion of subjects achieving VLDA at Week 16
  - Change in quality of life as assessed by SF-36 total score, physical component summary (PCS), and mental component summary (MCS) change from baseline to Weeks 16
  - Proportion of subjects achieving individual MDA components at Week 16 as compared to baseline
- To investigate the relationship between ACR50 response and other factors
  - Association of baseline positive WPI  $\geq 7$  with ACR50 response
- To investigate that the 80 mg Q4W regimen is efficacious compared to placebo, as measured by the same primary, secondary and exploratory endpoints
- To compare the three regimens of izokibep for assessment of dose-response relationships, as measured by the primary and secondary endpoints
- To evaluate the pharmacokinetics of izokibep in subjects with PsA
- To evaluate the immunogenicity of izokibep in subjects with PsA

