- Change from baseline in SF-36 total score, PCS, and MCS at Weeks 16, 24, and 52
- Change from baseline in FACIT-F at Weeks 16, 24, and 52
- Change from baseline in LEI enthesitis score at Weeks 16, 24, and 52 in those with enthesitis at baseline (LEI>0)
- HAQ-DI change from baseline to Weeks 24 and 52
- HADS change from baseline to Week 24 and 52

Change from baseline for the individual components of the ACR and MDA scores will be summarized at Week 16. Summary statistics (n, mean, standard deviation, median, minimum, and maximum) will be provided

- Swollen Joint Count
- Tender Joint Count
- SAPVAS
- SGADA
- IGADA
- HAQ-DI
- CRP
- PASI
- BSA
- Tender enthesal points  $\leq$  1 site out of 6 sites included in LEI

The following will be analyzed with a time to event model, using a log rank test with stratification by the factors used to stratify randomization. Subjects who do not achieve the endpoint at or before the week 16 visit will be censored at the time of the last assessment could be derived at or before week 16.

- Time to resolution of enthesitis (LEI = 0) among subjects with enthesitis (LEI = 0) at baseline.
- Time to first achievement of ACR50

- Time to first achievement of PASI90 among subjects with  $\geq 3\%$  BSA psoriasis at baseline
- Time to first achievement of MDA
- Time to first achievement of ACR20
- Time to first achievement of PsAID improvement of at least 3 among subjects with PsAID  $\geq 3$  at baseline
- Time to first achievement of PASI100 among subjects with PsAID  $\geq 3$  at baseline

WPI will be calculated at baseline. WPI is a scale of 0-19, and is a count of how many of 19 body sites the subject reports pain or tenderness in the prior 7 days. Standard summary statistics for binary data will be calculated by baseline WPI (WPI  $\geq 7$  vs.  $< 7$ ) for the following endpoints:

- ACR50 at week 16 (observed responder, observed non-responder, missing)
- LEI responders at week 16 (observed responder, observed non-responder, missing)
- PsAID at week 16 (observed responder, observed non-responder, missing)
- HAQ-DI at week 16: improvement of at least 0.35 (observed responder, observed non-responder, missing)

Area under the curve (AUC) for ACR-N will be calculated for each subject by triangulating the observed values at baseline (by definition ACR-N = 0 at baseline) and weeks 2, 4, 12 and 16. The area for consecutive visits, using nominal time from Week t and Week u, will be calculated as

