### 6.6.6. Subgroup Analysis

Various subgroup analyses of the efficacy data will be reported. These analyses will investigate the treatment response within specific subgroups of interest, and assess whether the treatment response is consistent across different subgroup levels. All analyses will be performed on the FAS data set. Treatment effect will be summarized by comparison (QW versus placebo; Q2W versus placebo) and presented in tables and a forest plot.

Summaries of primary and secondary efficacy endpoints will be presented by subgroup:

The following subgroups are of interest for the primary and all secondary endpoints:

- Race (Asian, White, Black or African American, other)
- Sex (male, female)
- Age (< 65, ≥ 65)
- Prior TNFi use (Yes/No)

The following subgroups are also of interest for ACR50 at Week 16 and all secondary endpoints:

- Any csDMARD at Baseline (Yes/No)
  - MTX only
  - MTX + other csDMARD
  - Non-MTX csDMARD only
  - No csDMARD at baseline
- Any prior TNFi exposure (Yes/No)
- Prior TNFi failure (Yes/No)
- Number of prior failed biologics group (0, 1, 2 or more)
- Geographic region
  - North America (US or Canada)
  - Europe (Bulgaria, Czech Republic, Spain, Hungary, Poland or Germany)
  - Non-US (Bulgaria, Czech Republic, Spain, Hungary, Poland, Germany or Canada)
- Country
  - United States
  - Canada
  - Bulgaria
  - Czech Republic
  - Poland
  - Hungary
  - Spain
  - Germany
- BMI ( $\leq 18$ ,  $> 18 - \leq 25$ ,  $> 25 - \leq 30$ ,  $> 30 - \leq 35$ ,  $> 35$ )
- Smoking status (never, former, current)

- Enthesitis at baseline
  - LEI = 0
  - LEI > 0
  - LEI = 1
  - LEI = 2
  - LEI = 1 or 2
  - LEI < 3
  - LEI  $\geq$  3
  - LEI < 4
  - LEI  $\geq$  4
- Combination of enthesitis and prior TNFi exposure
  - LEI = 1 or 2 and no prior TNFi exposure
  - LEI  $\geq$  3 and no prior TNFi exposure
  - LEI = 1 or 2 and prior TNFi exposure
  - LEI  $\geq$  3 and prior TNFi exposure

The following endpoints are of interest for the subjects with enthesitis at baseline (LEI > 0) and subjects without enthesitis (LEI = 0) at baseline:

- PsAID response at Week 16
- PsAID change from baseline to Week 16
- HAQ-DI response at Week 16
- HAQ-DI change from baseline to Week 16
- Change in DAPSA and cDAPSA from baseline to Week 16
- VLDA at Week 16
- Change in SF-36 total score, physical component summary (PCS), and mental component summary (MCS) from baseline to Week 16
- MDA at Week 16 (including each component of MDA)

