The following subgroups are of interest for summarizing Time to resolution of enthesitis (LEI = 0) among subjects with enthesitis (LEI = 0) at baseline.

- Sex (male, female)
- Prior exposure to TNFi (yes, no)
- LEI score at baseline
  - LEI = 1
  - LEI = 2
  - LEI = 1 or 2
  - LEI  $\geq$  3

The following subgroup is of interest for the endpoints of PASI75, PASI90 and PASI100:

- Baseline BSA 10% or greater

Response rates and difference in response rate will be reported for each subgroup. Cochran-Mantel-Haenszel weighting will be used to calculate a 95% CI for subgroup analyses for each endpoint similar to Section 6.6.1 and 6.6.3 using stratified tests. A forest plot for the difference in response rate and 2-sided 95% CI will also be presented. No p-values will be reported for the subgroup analyses.

PsAID and HAQ-DI response rates will be determined by the proportion of subjects who achieve at least a minimum clinically important difference (MCID) improvement from baseline to Week 16. MCID values are 3 units for PsAID and 0.35 units for HAQ-DI.

Similar to the subgroup analysis above, difference in response rate and 2-sided Cochran-Mantel-Haenszel weighted stratified 95% CI will be reported for subgroup analyses for each binary endpoint.

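### SAP 6.6.6 defines HAQ-DI response without the baseline minimum that the protocol and SAP 2.2.3 set for the same endpoint, leaving two denominators for the enthesitis subgroup tables

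*SAP*

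**What the plan says.** Two definitions of Week 16 HAQ-DI response stand side by side.

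- **With a baseline minimum.** SAP 2.2.3, for the enthesitis subpopulation: "Proportion of subjects with a HAQ-DI decrease of at least 0.35 at Week 16 compared to baseline in subjects with HAQ-DI" above 0.35 at baseline. The protocol has the same restriction in its Synopsis and again in Section 3, where the objective is worded as a decrease "compared to baseline in subjects with HAQ-DI >0.35 at baseline".
- **Without one.** SAP 6.6.6 introduces a list that includes HAQ-DI response and PsAID response at Week 16: "The following endpoints are of interest for the subjects with enthesitis at baseline (LEI > 0) and subjects without enthesitis" at baseline. It says of the subgroup work that "All analyses will be performed on the FAS data set". It then defines response: "PsAID and HAQ-DI response rates will be determined by the proportion of subjects who achieve at least a minimum clinically important difference (MCID) improvement", adding that "MCID values are 3 units for PsAID and 0.35 units for HAQ-DI". It states no baseline condition.

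SAP 3.2.2 names endpoints that are analysed in a subset of the full analysis set and sends the other secondary and exploratory endpoints to the full set. HAQ-DI response is not among those named. SAP 2.6 lists HAQ-DI change as an exploratory variable but not HAQ-DI response. The WPI summary in SAP 6.6.5 also gives only the threshold: "HAQ-DI at week 16: improvement of at least 0.35".

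PsAID differs. Its minimum of 3 at baseline appears in SAP 2.5, 3.2.2, 6.6 and 6.6.3, and 3.2.2 explains that subjects must be able to reach the endpoint.

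**The concern.** For LEI > 0, SAP 2.2.3 and 6.6.6 describe the same quantity with different denominators. For LEI = 0, 6.6.6 is the only definition, because the restricted wording is tied to the enthesitis subpopulation. Entry (Protocol 5.1) requires at least 3 swollen and 3 tender joints but sets no HAQ-DI minimum, so subjects with very low disability can be randomized. Without the minimum they are certain non-responders on every treatment.

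The subgroup analyses are meant to show whether the treatment response is consistent across subgroup levels. A denominator that includes subjects who cannot respond makes each risk difference depend on the baseline mix as well as on the treatment effect. If that mix differs by LEI group, or if a programmer follows 2.2.3 for LEI > 0 and 6.6.6 for LEI = 0, the two risk differences are not comparable.

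**Working it through.** The documents give no rate, sample size or power for HAQ-DI response, so there is no planned figure to reproduce.

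**Step 1: who cannot respond.** SAP Appendix 2.1 scores HAQ-DI as the sum of category scores (0 to 3) divided by the number of categories answered (6 to 8). The attainable values below 0.35 are:

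- 8 categories: 0, 0.125, 0.25
- 7 categories: 0, 0.143, 0.286
- 6 categories: 0, 0.167, 0.333

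The score cannot go below 0, so none of these can fall by 0.35. No attainable score equals 0.35. The rule of baseline above 0.35 therefore removes exactly the subjects who cannot respond.

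**Step 2: dilution.** Let s be the share of a subgroup with baseline HAQ-DI above 0.35, balanced between arms by randomization. The others respond at 0% in both arms, so

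RD(all) = s × RD(eligible).

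**Step 3: illustration.** Everything here is assumed except the group sizes. Those follow the SAP 2.3 expectation of up to 60% with enthesitis: about 60 (LEI > 0) and 40 (LEI = 0) of 100 per arm. Assumed response among eligible subjects is 30% on placebo and 60% on izokibep in both LEI groups, so RD(eligible) = 0.30 and the true gap is 0. The TNFi strata are ignored. The variance of each subgroup difference is [p0(1 − p0) + p1(1 − p1)]/n, with p0 = 0.30s and p1 = 0.60s. The SE of the gap is the square root of the sum of the two variances.

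| s, LEI > 0 / LEI = 0 | RD, LEI > 0 | RD, LEI = 0 | Gap | SE of gap |
|---|---|---|---|---|
| 1.00 / 1.00 (minimum applied to all) | 0.300 | 0.300 | 0 | 0.137 |
| 0.90 / 0.90 | 0.270 | 0.270 | 0 | 0.136 |
| 0.95 / 0.85 | 0.285 | 0.255 | 0.030 | 0.136 |
| 0.95 / 0.75 | 0.285 | 0.225 | 0.060 | 0.134 |
| 0.90 / 0.60 | 0.270 | 0.180 | 0.090 | 0.130 |
| 0.80 / 0.90 | 0.240 | 0.270 | −0.030 | 0.135 |

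The first row's SE takes every subject as eligible. Applying the minimum when some are not leaves fewer subjects and a larger SE.

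**Step 4: real heterogeneity.** With equal shares of 0.90 and true differences of 0.40 and 0.20, the table shows 0.36 and 0.18, so a real gap of 0.20 becomes 0.18. With true differences of 0.25 (LEI > 0) and 0.30 (LEI = 0) and shares of 0.95 and 0.75, it shows 0.95 × 0.25 = 0.238 and 0.75 × 0.30 = 0.225, so the order reverses.

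**Step 5: mixed definitions.** If the minimum is applied in LEI > 0 only, a gap appears even with equal shares. With RD(eligible) = 0.30 and 0.90 eligible in both groups, the table shows 0.300 and 0.90 × 0.30 = 0.270, a gap of 0.030. With 0.75 eligible in LEI = 0 it shows 0.300 and 0.225, a gap of 0.075.

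**The case against.** The best defence is that 6.6.6 supplies thresholds only and relies on definitions given elsewhere. SAP 2.2.3 labels the restricted version as the Week 16 response to HAQ-DI, so the later list may simply reuse a defined term. The default in 3.2.2 cannot be taken literally: it also leaves out the dactylitis, nail and SPARCC restrictions that SAP 2.6 imposes. The lists in 6.6.5 drop known restrictions too, for example for PASI75 and for PsAID response at Weeks 24 and 52.

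This makes a restricted denominator the likelier intention, but it does not settle the text. The 6.6.6 sentence says how the response rate is determined. For HAQ-DI, no statistical-methods section restates the minimum, and for LEI = 0 no other definition exists to fall back on.

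Three further points for the defence stand. Within each LEI group, the literal version is still a valid randomized comparison, for an unrestricted population. HAQ-DI change from baseline is reported in both LEI groups and needs no threshold. The illustrated gaps are all smaller than one standard error of the contrast.

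A reader might infer that PsAID response is redefined as well. The SAP does not support that. Section 3.2.2 sets the PsAID minimum as a subset of the full analysis set, so the full-set sentence in 6.6.6 does not cancel it. The omission there needs only a cross-reference. A reader might also infer that a treatment-effect contrast by WPI is affected, but 6.6.5 specifies only descriptive response summaries by WPI category, with no treatment difference.

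**Conclusion.** The conflict is real for HAQ-DI response. One Week 16 endpoint in the LEI > 0 subgroup has two denominators, and the literal 6.6.6 version shrinks every subgroup risk difference by the eligible share. That step rests only on the scoring rule and on randomization.

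It is tempting to conclude that the LEI > 0 versus LEI = 0 contrast is distorted, with the effect made to look larger in enthesitis. The documents do not support that. A false gap needs either unequal eligible shares or the two definitions applied to different LEI groups, and baseline shares are not given. In the range assumed, unequal shares produce gaps from −3 to +9 points, equal shares produce none, and mixed definitions produced 3 and 7.5 points in the two cases shown. The sound conclusion is that the contrast can be distorted, by an unknown amount and in an unknown direction.

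The reach is limited. Subgroup results carry estimates and intervals without p-values. HAQ-DI response is not in the alpha-controlled sequence, the PsAID test in that sequence keeps its minimum, and the primary endpoint is untouched.

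**What to change.** - In SAP 6.6.6, state that HAQ-DI response is assessed in subjects with baseline HAQ-DI above 0.35, in both LEI groups.
- Add HAQ-DI response to the restricted endpoints in SAP 3.2.2.
- In 6.6.6, cross-refer to the existing PsAID minimum of 3 at baseline, as a clarification only.
- Use the same HAQ-DI denominator in the WPI summary in 6.6.5.
- Report the number eligible per arm and subgroup. If an unrestricted version is also wanted, label it as such and show both.

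This takes a few sentences and applies a minimum that the documents already contain. The cost is smaller denominators, and so somewhat wider intervals, in exploratory tables.

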## 6.7. Safety

For all Safety Tables, data will be summarized as follows, unless otherwise specified:

- Period 1 will include the first 16 weeks, summarized by the randomized treatment arms (Placebo QW; Izokibep QW; Izokibep Q2W, Izokibep Q4W)
- Period 2 will include data after Week 16 visit, summarized by the randomized treatment groups (Placebo - Izokibep QW; Izokibep QW; Izokibep Q2W, Izokibep Q4W)
  - Selected AE summaries will be presented as: Period 2 will include data after Week 16 visit, summarized by Placebo - Izokibep QW; Izokibep QW (those who receive QW during any part of period 2); Izokibep Q2W (those who receive Q2W during any part of period 2); Izokibep Q4W (those who receive Q4W during any part of period 2); Izokibep QW only (those who receive only izokibep QW during period 2); Izokibep Q2W only (those who receive only izokibep Q2W during period 2); Izokibep Q4W only (those who receive only izokibep Q4W during period 2)

